#### **6.2.6.2. ADA titer**

For patients who are ADA ever positive, the maximum observed ADA titer for a patient will be summarized, overall and by ADA subcategories (baseline ADA positive, treatment-boosted ADA, treatment-induced ADA, transient ADA response, persistent ADA response) of patients having each discrete maximum titer value will be tabulated. The denominator to calculate the percentages will be the total number of patients in the associated ADA subcategory.

For patients with treatment-induced ADA, a cross tabulation of duration of ADA response and maximum ADA titer will be provided. The following categories for duration of ADA response will be used:  $\leq 1$ ,  $> 1$  to  $\leq 3$ ,  $> 3$  to  $\leq 5$ ,  $> 5$  to  $\leq 7$ ,  $> 7$  to  $\leq 13$ ,  $> 13$  to  $\leq 16$ ,  $> 16$  to  $\leq 25$ ,  $> 25$  weeks. In this categorization, the censoring in duration of ADA response is ignored.

#### **6.2.6.3. Analysis of PK and safety by immunogenicity status**

The following ADA and nAb status will be used for the analyses described below.

ADA

- ADA ever-positive versus ADA never-positive
- ADA: treatment-induced ADA versus ADA never-positive or baseline ADA positive

### nAb

- nAb ever-positive versus nAb never-positive
- nAb: treatment-induced nAb versus nAb never-positive or baseline nAb positive

### PK parameters and immunogenicity status

The following analyses will include patients in both the immunogenicity analysis set and in the PK parameter analysis set. The PK endpoints pertinent to the immunogenicity analyses are  $C_{trough}$  and  $C_{max}$ .

Blood samples for avelumab PK will be collected pre-dose and post-dose on Cycle 1 Day 1 and Day 15, Cycle 2 Day 1, and pre-dose on Day 15 of Cycles 3, 6, 9 and 12.

$C_{trough}$  and  $C_{max}$  will be summarized descriptively (n, mean, SD, CV, median, minimum, maximum, geometric mean, its associated CV, and 95% CI) by nominal time and ADA status. Linear-linear box plots of mean and median for  $C_{trough}$  and  $C_{max}$  over nominal time and by ADA status will be presented, as data permit.

Among patients with treatment-induced ADA, analyses will be conducted to assess whether  $C_{trough}$  and  $C_{max}$  have any changes before and after the first positive ADA assessment. To be included in this analysis, patients must have the same PK parameter available both before and after the first positive ADA assessment. Relative PK day will be calculated as:

$$(\text{PK assessment nominal day}) - (\text{first positive ADA assessment nominal day}).$$

Nominal day is the protocol scheduled timing for an assessment. For example, if  $C_{trough}$  is collected on Day 1 of Cycle 2 and the first positive ADA result is observed on Day 1 of Cycle 3, then the relative PK day for this  $C_{trough}$  is -28.

As data permit, the analyses described above will be repeated for nAb.

### Safety and immunogenicity status

The following analyses will include patients in the immunogenicity analysis set.

The frequency (number and percentage) of patients with each of the following will be presented by ADA status.

- TEAEs, by SOC and PT
- TEAEs leading to dose reduction of avelumab, by SOC and PT
- TEAEs leading to discontinuation of avelumab, by SOC and PT
- TEAEs leading to discontinuation of study treatment by SOC and PT

- Grade  $\geq$  3 TEAEs, by SOC and PT
- SAEs, by SOC and PT
- IRRs, by PT

For patients who had at least one IRR and have treatment-induced ADA, time related to first onset of an IRR (infusion 1, infusion 2, infusion 3, infusion 4 or later) will be summarized taking into account whether the IRR occurred on or after the first ADA positive assessment or whether the IRR occurred before the first ADA positive assessment.

As data permit, the analyses described above will be repeated for nAb.

CCI

#### **6.4. Subset Analyses**

OR and DR (if meaningful) will also be summarized for patients in the following subsets:

Within each cohort:

- Baseline PD-L1 status: Positive, Negative.

NSCLC cohort:

- Histology: Non-Squamous, Squamous;
- Number of previous systemic therapies: 1,  $\geq$ 2.

UC cohort:

- Baseline ECOG performance status (PS):  $\leq 1, \geq 2$ .

In the case of a low number of patients within a category (<10 patients), the category may not be summarized.

## 6.5. Baseline and Other Summaries and Analyses

### 6.5.1. Baseline summaries

The following analyses will be based on the FAS by treatment group.

#### 6.5.1.1. Demographic characteristics

Demographic characteristics will be summarized by treatment group using the following information from the 'Screening/Baseline Visit' eCRF pages.

- Demographic characteristics
  - Gender: Male, Female
  - Race: White, Black or African American, Asian, American Indian or Alaska Native, Native Hawaiian or Other Pacific Islander, Multiracial, Not Reported.
  - Ethnic origin:
    - Hispanic or Latino
    - Not Hispanic or Latino
  - Age (years): summary statistics
  - Age categories:
    - $< 65$  years,  $\geq 65$  years
    - $< 65, 65-75, 75-85, \geq 85$  years
  - Pooled Geographical Region (as applicable):
    - North America
    - Europe
    - Asia
    - Rest of the World (Australasia, Latin America, Africa and/or Middle East will be included as additional pooled geographical regions if including  $> 10\%$  of the overall treated population)
  - Geographic Region (as applicable):
    - North America
    - Latin America
    - Western Europe
    - Eastern Europe
    - Middle East

- Australasia
- Asia
- Africa
- Eastern Cooperative Oncology Group (ECOG) Performance Status: 0, 1, 2, 3, and 4

Center codes will be used for the determination of the patient's geographic region.

The listing of demographics and baseline characteristics will include the following information: patient identifier, treatment group, age, sex, race, ethnicity and ECOG performance status.

#### **6.5.1.2. Medical history**

Medical history will be coded using the most current available version of Medical Dictionary for Regulatory Activities (MedDRA) and will be summarized from the 'Medical History' eCRF page. Medical history will be summarized as the numbers and percentages of patients by MedDRA preferred term (PT) as event category and MedDRA primary system organ class (SOC) as summary category. Each patient will be counted only once within each PT or SOC.

Medical history will be displayed in terms of frequency tables: ordered by primary SOC and PT in alphabetical order.

For the UC cohort, the reasons for ineligibility for cisplatin-containing front-line chemotherapy will be summarized using information collected on 'Oncology Stratification By Inclusion Criteria' and 'ECOG Performance Status' eCRF pages:

- Baseline ECOG PS 2;
- Renal dysfunction (defined as creatinine-clearance <60 ml/min) at baseline;
- Grade  $\geq 2$  peripheral neuropathy at baseline;
- Grade  $\geq 2$  hearing loss (hearing loss measured by audiology of 25 decibels at two contiguous frequencies) at baseline.

#### **6.5.1.3. Disease characteristics**

Information on disease characteristics collected on 'Primary Diagnosis' and RECIST eCRF pages will be summarized by treatment group. Summary statistics will be presented for the following.

From the 'Primary Diagnosis' eCRF page:

- Site of primary tumor
- Primary diagnosis (summarize all categories collected in the 'Primary Diagnosis' eCRF page)

- Time since initial diagnosis to date of first dose of study treatment (months), defined as (date of first dose of study treatment – date of initial diagnosis)/30.4375

From the RECIST eCRF page:

- Measurable disease (lesions) at baseline (Yes, No)
- Involved tumor sites at baseline

Listing of disease history will be provided with all relevant data (as collected on the ‘Primary Diagnosis’ eCRF page) and derived variables as above.

#### **6.5.1.4. Prior anti-cancer therapies**

The prior anti-cancer therapies are collected under the ‘Prior Cancer Therapy’, ‘Prior Radiation Therapy’ and ‘Prior Anti-Cancer Surgery’ eCRF pages.

The number and percentage of patients in each of the following anti-cancer therapy categories will be tabulated:

- Patients with at least one type of prior anti-cancer therapy
- Patients with at least one prior anti-cancer drug therapy
- Patients with at least one prior anti-cancer radiotherapy
- Patients with at least one prior anti-cancer surgery

Prior anti-cancer drug therapy will be summarized as follows based on the number and percentage of patients with the following:

- At least one prior anti-cancer drug therapy
- Number of prior anti-cancer drug therapy regimens: missing, 1, 2, 3,  $\geq 4$
- Intent of Drug Therapy: Neo-Adjuvant, Adjuvant, Advanced – Metastatic, Locoregional Disease-Recurrence
- Best response: CR, PR, SD, PD, Unknown, Not applicable. Best response is derived from the last treatment regimen.

The prior anti-cancer drug therapies will also be summarized based on the number and percentage of patients by the drug class and preferred term. A patient will be counted only once within a given drug class and within a given drug name, even if he/she received the same medication at different times. The summary will be sorted on decreasing frequency of drug class and decreasing frequency of drug name in a given drug class. In case of equal frequency regarding drug class (respectively drug name), alphabetical order will be used.

Prior anti-cancer drug therapies will be included in the listing that follow with a flag to identify prior therapies. These will include the patient identification number, and all the relevant collected data-fields on the corresponding eCRF pages.

- Listing of anti-cancer drug therapies

## 6.5.2. Study conduct and patient disposition

The following analyses will be performed based on the FAS by treatment group.

### 6.5.2.1. Patient disposition

The percentages below will be calculated based on the number of patients in the FAS.

- Total number of patients screened overall
- Number of patients who discontinued from the study prior to treatment with study drug overall and by the main reason for discontinuation
- Number and percentage of treated patients in each of the analysis sets defined in Section 4
- Number and percentage of patients with study drug ongoing (separately for each study drug administered in combination)
- Number and percentage of treated patients who discontinued study drug overall and by the main reason for discontinuation of study drug (separately for each study drug administered in combination)
- Number and percentage of patients who entered follow-up
- Number and percentage of patients who discontinued follow-up overall and by the main reason for discontinuation

In addition, the following will be summarized:

- Number and percentage of treated patients overall, by region (Europe, EEA (required by EudraCT), North America, Latin America, Middle East, Asia, Australasia, Africa), by country within region
- Number and percentage of treated patients by center

In addition, a cross tabulation of patients who have discontinued/are ongoing treatment with avelumab vs patients who have discontinued/are ongoing treatment with axitinib will also be provided.

### 6.5.2.2. Protocol deviations

All protocol violations that impact the safety of the patients and/or the conduct of the study and/or its evaluation will be reported. These include:

- Patients who are dosed on the study despite not satisfying the inclusion criteria
- Patients who develop withdrawal criteria whilst on the study but are not withdrawn
- Patients who receive the wrong treatment or an incorrect dose
- Patients who receive an excluded concomitant medication
- Deviations from GCP.

The identification of these and other CSR-reportable deviations will be based on the inclusion/exclusion criteria or other criteria presented in the protocol.

### **6.5.3. Study treatment compliance and exposure**

The following analyses will be based on the safety analysis set by treatment group.

Cycle definitions for study drugs that are administered in combination apply to all the study drugs in the combination. Ie, cycle is patient-dependent, rather than study-drug-dependent when study drugs are administered in combination.

For Cycle X, actual cycle start date for each patient is

- the earliest start date of dosing in the Cycle X day 1 visit eCRF exposure page, if the patient received study treatment on that visit (ie, any study drug with dose>0 at that visit)
- the first day of assessments in the Cycle X day 1 visit, if the patient did not receive study treatment on that visit (ie, all study drugs had dose=0 at that visit). Use start date in the exposure page if available; if start date is not available then use date of collection of vital signs on Cycle X day 1 visit.

Actual cycle end date for each patient is,

- for all cycles X except the last cycle, actual cycle end date = actual cycle (X+1) start date – 1 day;
- for the last cycle, actual cycle end date = actual cycle start date + 28 (in days) – 1 day

**Cycle duration (weeks)** = (actual cycle end date – actual cycle start date + 1)/7

When summarizing exposure for each study drug, only cycles from first dose of study treatment until the last cycle with non-zero dose of at least one of the study drugs should be included.

Exposure may be summarized (per cycle and/or overall) as dose received (cumulative dose, actual dose intensity) and as dose received relative to intended dose (relative dose intensity [RDI]).

The formulae below should be applied to each study drug separately even when study drugs are administered in combination.

The derivations below are provided for the following study drugs (administered alone or in combination):

- Avelumab administered as a 1-hour IV infusion at a dose of 800 mg once every 2 weeks in 4-week cycles.
- Axitinib administered orally at a dose of 5 mg BID.

#### **6.5.3.1. Exposure to avelumab**

The dose level for avelumab is calculated as actual dose administered (mg).

**Intended duration of treatment with avelumab (weeks) =**

(end date–date of first dose of avelumab +1)/7,

where end date = start date of last cycle with non-zero dose of avelumab + 28 – 1

**Duration of exposure to avelumab (weeks) =**

(last dose date of avelumab – first dose date of avelumab + 14)/7

**Cumulative dose** is the sum of the actual doses of avelumab received.

**Actual Dose Intensity (DI)**

- Overall actual DI (mg/4-week cycle) = [overall cumulative dose (mg)] / [intended duration of treatment with avelumab (weeks)/4].

**Relative Dose Intensity (RDI)**

- Intended DI (mg/4-week cycle) = [intended cumulative dose per cycle] / [intended number of 4-weeks in a cycle] = [2 x 800 (mg)] / [1 (4-week cycle)] = 1600 (mg/4-week cycle)
- Overall RDI (%) =  $100 \times [\text{overall actual DI}] / [\text{intended DI}]$   
=  $100 \times [\text{overall actual DI}] / [1600 \text{ (mg/4-week cycle)}]$

#### **6.5.3.2. Exposure to axitinib**

The dose level is calculated as actual dose administered (mg/day).

**Intended duration of treatment with axitinib (weeks) =**

(last dose date of axitinib– date of first dose of axitinib +1)/7,

**Duration of exposure to axitinib (weeks) =**

(last dose date of axitinib – first dose date of axitinib + 1)/7

**Overall cumulative dose** is the sum of the actual doses of axitinib received in the study.

**Actual Dose Intensity (DI)**

- Overall actual DI (mg/week) = [overall cumulative dose (mg)] / [intended treatment duration (weeks)]

**Relative Dose Intensity (RDI)**

- RDI (%) =  $100 \times [\text{overall cumulative dose}] / [\text{intended cumulative dose per week} \times \text{number of weeks from first dose of study drug to last dose of study drug}]$   
=  $100 \times [\text{overall cumulative dose}] / [7 \times 2 \times 5 \times \text{duration of exposure to axitinib in weeks}]$

### **6.5.3.3. Dose reductions**

Applicable to avelumab. Dose reduction is defined as actual non-zero dose < 90% of the planned dose.

Applicable to axitinib. Dose reduction is defined as a change to a non-zero dose level lower than that planned in the protocol.

The number and percentage of patients with at least one dose reduction as well as a breakdown of the number of dose reductions (1, 2, 3,  $\geq 4$ ) will be summarized.

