	2 systolic BP readings separated by at least 1 hour show systolic pressure >160 mm Hg OR 2 diastolic BP readings separated by at least 1 hour show diastolic pressure >105 mm Hg	
 
Withhold until BP is less than 150/100 mm Hg and adjust antihypertensive medication.
 
Then, reduce by 1 dose level and resume treatment.
 
If axitinib dosing is temporarily discontinued, patients receiving antihypertensive medications should monitor closely for hypotension. The plasma half-life of axitinib is 2-4 hours and BP usually decreases within 1-2 days following dosing interruption.
 
See Section 5.5.5.2 for monitoring/management of axitinib-related hypertension.
 
	
 
Continue as per schedule.
 

	Recurrent hypertension following previous dose reduction (2 systolic BP readings separated by at least 1 hour show systolic pressure >150 mm Hg) OR Recurrent diastolic BP >100 mm Hg (2 BP readings separated by at least 1 hour) following previous dose reduction	
 
Repeat dose reduction by one lower dose level.
 
See Section 5.5.5.2 for monitoring/management of axitinib-related hypertension.
 
	
 
Continue as per schedule.
 

**Table 4 Axitinib Dose Modifications and Avelumab Infusion Omissions for Investigational Product-Related Toxicity (continued)**

Toxicity	NCI CTCAE Severity Grade	Axitinib	Avelumab
		Dose Modification	Treatment Modification
Infusion-related Reaction	Grade 1-4	
 
Continue at the same dose level.
 
	See Section 5.5.5.5 and Table 5 .
Immune-related AE (irAE)	Grade 1-4	
 
Grade 1: continue at the same dose level.
 
Grade 2-4: hold treatment until recovery to Grade <math>\leq 1</math> and restart axitinib at the same dose level for Grade 2 and at reduced dose level for Grade 3-4.
 
	See Section 5.5.5.6 and Table 6 .
Stevens-Johnson syndrome	Grade 3-4	
 
Permanent discontinuation
 
	
 
Permanent discontinuation
 

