## 3.4. Baseline Variables

### 3.4.1. Study drug, study treatment and baseline definitions

In this study, ‘**study drug**’ refers to avelumab or axitinib and ‘**study treatment**’ (or ‘**treatment group**’) refers to one of the following:

- NSCLC Cohort: avelumab 800 mg IV Q2W plus axitinib 5 mg PO BID;
- UC Cohort: avelumab 800 mg IV Q2W plus axitinib 5 mg PO BID.

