### **6.5.3.4. Dose escalations**

Applicable to axitinib only.

Dose escalation is defined as a change to a dose level higher than that planned in the protocol.

Number and percentage of patients with at least one dose escalation as well as a breakdown of dose escalations (1, 2, 3,  $\geq 4$ ) will be summarized.

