### **6.5.3.5. Dose interruptions**

Applicable to axitinib only.

An interruption is defined a 0 mg dose administered on one or more days for axitinib. What follows defines how dose interruptions will be counted in the case of multiple dose interruptions.

- If an interruption occurs consecutively for at least two days, then it will be counted only once (example: If the actual dose on days 1-3 is 10 mg and actual dose on days 4-5 is 0 mg, then the total number of dose interruptions is 1).
- If an interruption occurs for more than one day, but the days are not consecutive, ie there is at least one dosing day in between, then each dose interruption will be counted as a different occurrence (example: If the actual dose on days 1, 3 and 5, is 10 mg and actual dose on days 2 and 4 is 0 mg, the total number of dose interruptions is 2).

A dose interruption is not considered a dose reduction.

The number and percentage of patients with dose interruptions and the corresponding reasons will be summarized.

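### SAP 6.5.3.3 and 6.5.3.4 classify an axitinib dose change by where the new dose lies relative to the planned dose, not by its direction, so read literally 10 to 7 mg BID counts as an escalation and 2 to 3 mg BID as a reduction

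*SAP*

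**What the plan says.** For axitinib, SAP 6.5.3.3 says: "Dose reduction is defined as a change to a non-zero dose level lower than that planned in the protocol". SAP 6.5.3.4 says: "Dose escalation is defined as a change to a dose level higher than that planned in the protocol". The outputs are "The number and percentage of patients with at least one dose reduction as well as a breakdown of the number of dose reductions" and "Number and percentage of patients with at least one dose escalation as well as a breakdown of dose escalations", each with categories 1, 2, 3 and at least 4.

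Neither section names the planned dose. SAP 3.4.1 gives the regimen as "NSCLC Cohort: avelumab 800 mg IV Q2W plus axitinib 5 mg PO BID", with the same doses for the UC cohort. SAP 6.5.3 repeats 5 mg BID, and the relative dose intensity formula in SAP 6.5.3.2 uses 7 x 2 x 5 mg per week.

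Protocol Table 3 lists five levels: 2, 3, 5, 7 and 10 mg BID. Protocol 5.5.5.1 allows increases and toxicity-related decreases one level at a time, and a return to the previous level after a reduction, which it calls re-escalation. Protocol Table 4 uses reduction in the stepwise sense: "Repeat dose reduction by one lower dose level". Protocol 5.9.1 provides for further changes with strong CYP3A4/5 inhibitors or inducers, including a cut to about half the dose.

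**The concern.** A reduction or escalation has a direction, but the SAP rule has none. It looks at where the patient lands, not where the patient came from. With only one level on each side of the planned dose this would not matter. With two on each side, a patient can move down and still be above 5 mg, or move up and still be below it. The rule then gives the opposite label, and the event goes into the wrong table.

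The counts of reductions and escalations describe how well the combination was tolerated, and safety and tolerability is a secondary objective. A decrease tabulated as an escalation misdescribes that patient's course.

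**Working it through.** The plan states no figure for this point, so the check applies the two definitions to the moves that the protocol allows.

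**Inputs.** Levels 2, 3, 5, 7, 10 mg BID (Protocol Table 3). Planned dose 5 mg BID (SAP 3.4.1, 6.5.3, 6.5.3.2). SAP rule: reduction if 0 < new < 5; escalation if new > 5; otherwise not counted.

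**Step 1: the eight one-level moves.**

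| Move (mg BID) | Direction | SAP label |
|---|---|---|
| 5 to 7 | up | escalation |
| 7 to 10 | up | escalation |
| 5 to 3 | down | reduction |
| 3 to 2 | down | reduction |
| 10 to 7 | down | **escalation** |
| 2 to 3 | up | **reduction** |
| 7 to 5 | down | not counted |
| 3 to 5 | up | not counted |

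Four labels agree with direction, two are opposite to it, and two moves are uncounted because they end at the planned dose.

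**Step 2: effect on the breakdowns.** Starting at 5 mg there are 2, 4, 6 and 12 one-level paths of 1, 2, 3 and 4 steps: 2 + 4 + 6 + 12 = 24. The comparison is the reading kindest to the SAP. It keeps the planned-dose reference but respects direction: a reduction is a downward move to below 5, an escalation an upward move to above 5. The breakdown differs on 6 of the 24 paths:

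| Path | Table | SAP count | Direction respected |
|---|---|---|---|
| 5-3-2-3 | reductions | 3 | 2 |
| 5-3-2-3-5 | reductions | 3 | 2 |
| 5-3-2-3-2 | reductions | 4 | 3 |
| 5-7-10-7 | escalations | 3 | 2 |
| 5-7-10-7-5 | escalations | 3 | 2 |
| 5-7-10-7-10 | escalations | 4 | 3 |

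On this reading the two at-least-one rows are right on all 24 paths. A patient at 10 mg already has an escalation, and a patient at 2 mg already has a reduction.

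**Step 3: moves outside the list.** Protocol 5.9.1 allows changes that are not one Table 3 level. Half of 5 mg is 2.5 mg. With 1 mg and 5 mg tablets (Protocol 5.4.1.2), a move from 5 to 2 mg BID is therefore possible, and the same section allows later adjustment. The path 5-2-3 is mislabelled at its second change: 2 reductions instead of 1. Half of 7 mg is 3.5 mg, which could become 4 mg BID, not a Table 3 level. The 24 paths are thus not every possible path.

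**Step 4: unit of dose level.** SAP 6.5.3.2 defines the axitinib dose level as the actual mg per day, and the example in 6.5.3.5 also works with daily amounts: "If the actual dose on days 1-3 is 10 mg and actual dose on days 4-5 is 0 mg". One missed dose at 10 mg BID gives 10 mg that day, the same as 2 x 5 mg. A daily amount cannot separate a missed dose from a change of level, so a corrected rule needs the prescribed dose.

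**The case against.** Three objections have weight.

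First, the two sections do not name 5 mg BID. If planned meant the currently prescribed level, the same words would label 10 to 7 mg a reduction and 2 to 3 mg an escalation, and nothing would be wrong. That reading is open, but no SAP text supports it and SAP 3.4.1, 6.5.3 and 6.5.3.2 point to 5 mg BID. A programmer might also follow the ordinary sense of the two words. The interruption section gives worked counting examples; these two give none.

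Second, comparison with the planned dose is a legitimate exposure measure. Relative dose intensity and the avelumab reduction rule both use it. This stands. A reader might infer that leaving a return to 5 mg uncounted is an error, or that the at-least-one percentages are wrong. The documents do not support that: if the measure is ever below or above the planned dose, those rows are right. Only under the protocol's stepwise usage does the at-least-one-reduction row miss paths such as 5-7-5 (7 of the 24), with the reduction count differing on 14. Those figures follow from a definition that the SAP did not choose.

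Third, the consequence is small. A one-level path needs three changes before a wrong label can appear, and Protocol 5.5.5.1 sets tolerability conditions for moving up. A reader might take 6 of 24 as a quarter of patients; it is a count of path types. A reader might also expect the tables of adverse events leading to dose reduction to be affected. They are not, because SAP 6.6.1 and 6.6.1.2 take those from the action recorded on the eCRF.

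**Conclusion.** Wrong as written; minor. Against a planned dose of 5 mg BID, the stated rule gives two permitted moves the label opposite to their direction. The event breakdowns are then wrong for patients who make those moves: 6 of the 24 one-level path types of up to four steps, plus some paths under Protocol 5.9.1. No number of patients or percentage-point effect can be stated, because the documents give no path frequencies. Objective response, the other efficacy endpoints, relative dose intensity and the eCRF-based adverse-event tables are untouched, and the SAP has no formal hypothesis test or decision rule. The conclusion rests on reading planned as 5 mg BID, which is the natural reading but is not spelled out in the two sections.

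**What to change.** In SAP 6.5.3.3 and 6.5.3.4, for axitinib:

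- Define a reduction as a change in the prescribed dose (mg BID) to a non-zero dose lower than the immediately preceding non-zero prescribed dose, whether or not it is a Table 3 level. Define an escalation likewise with higher.
- Count a return to a previous level after a reduction separately, as re-escalation.
- State that a missed or vomited dose is not a change of dose.
- Show changes made for CYP3A4/5 co-medication separately where the reason is recorded.
- If a summary against the planned dose is kept, label it ever below or ever above 5 mg BID.
- Add a worked counting example, as SAP 6.5.3.5 has for interruptions.

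With these rules 5-7-10-7 gives 2 escalations and 1 reduction, and 5-3-2-3 gives 2 reductions and 1 re-escalation.

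The cost is two reworded definitions, a few table rows and a small programming change. Protocol 5.5.5 and 5.5.2 say that dose modifications and missed or vomited doses are recorded in the CRF. The CRF is not among the documents, so it is an assumption that it holds the prescribed dose directly. The change concerns a counting rule only and alters no dosing rule.
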